**Table 1 Risk for Anifrolumab and Study Procedures**

Potential risk of clinical significance	Summary of data/rationale for risk	Mitigation strategy
Anifrolumab Risks		
Important Identified Risk: Herpes zoster Identified Risks Upper respiratory tract infection, bronchitis, respiratory tract infection, hypersensitivity, anaphylactic reaction, infusion-related reaction a	Refer to the IB for the most up-to-date safety data.	
Patients will be excluded from participation in the study if they have: recurrent or opportunistic infection requiring hospitalization and IV antibiotics; live or attenuated vaccine or clinically significant infection within 8 weeks prior to signing the ICF; history of a primary immunodeficiency, splenectomy, or any underlying condition that predisposes the participant to infection, or a positive HIV result; active HBV, HCV, CMV, or Epstein-Barr virus infection; severe HZ infection; or any infection requiring oral anti-infectives within 2 weeks prior to signing the ICF. See Section 3.2.
 
Infections, including non-opportunistic serious infections, opportunistic infections, TB, and latent TB will be monitored closely in this study. See Section 3.2, Section 5.2.6, and Section 6.3.
 
The incidence of severe allergic reactions has been low after IV administration of anifrolumab. Therefore, appropriate drugs and medical equipment to treat acute anaphylactic reactions will be immediately available, and site staff will be trained to recognize and treat anaphylaxis. See Section 3.2 and Section 6.10.1.

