### 1.3.3 Overall benefit: risk conclusion

Treatment with anifrolumab 300 mg IV Q4W was well tolerated, and had an acceptable safety profile in adult patients with moderate to severe SLE for up to 4 years of treatment.

Herpes zoster is an important identified risk for anifrolumab. Upper respiratory tract infection, bronchitis, respiratory tract infection, hypersensitivity, anaphylactic reaction, and infusion related reaction are identified risks for anifrolumab. Malignancy and serious infection are important potential risks for anifrolumab. Identified and important potential risks undergo careful enhanced monitoring in the development program. In addition to the ongoing blinded review provided by the study physician, an independent Data and Safety Monitoring Board (DSMB) will review blinded and unblinded safety data on a regular basis throughout the study (see Appendix A 6).

Overall, anifrolumab 300 mg as administered IV Q4W provides a favorable benefit-risk profile in the SLE population. Anifrolumab is the first-in-class type I IFN targeted therapy approved for the treatment of adult patients with moderate to severe SLE despite standard therapy.

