## Appendix S Anaphylaxis

In adults, anaphylaxis is highly likely when any 1 of the following 3 criteria is fulfilled:

1. Acute onset of an illness (minutes to several hours) with involvement of the skin, mucosal tissue, or both (e.g., generalised hives, pruritus or flushing, swollen lips, tongue and/or uvula)

AND AT LEAST ONE OF THE FOLLOWING:

- (a) Respiratory compromise (e.g., dyspnoea, wheeze-bronchospasm, stridor, reduced peak expiratory flow, hypoxaemia)
  - (b) Reduced BP (see number 3 below for definition) or associated symptoms of end-organ dysfunction (e.g., hypotonia [collapse], syncope, incontinence)
2. Two or more of the following that occur rapidly after exposure to a likely allergen for that patient (minutes to several hours):
    - (a) Involvement of the skin-mucosal tissue (e.g., generalised hives, itch, flush, swollen lips, tongue and/or uvula)
    - (b) Respiratory compromise (e.g., dyspnoea, wheeze-bronchospasm, stridor, reduced peak expiratory flow, hypoxaemia)
    - (c) Reduced BP (see number 3 below for definition) or associated symptoms (e.g., hypotonia [collapse], syncope, incontinence)
    - (d) Persistent gastrointestinal symptoms (e.g., crampy abdominal pain, vomiting)
  3. Reduced BP after exposure to known allergen for that patient (minutes to several hours); for adults a systolic BP of less than 90 mm Hg or greater than 30% decrease from that person's baseline BP (taken at or immediately prior to start of the infusion), whichever BP is lower.

The following definitions are provided for the purposes of this study:

**Hypersensitivity reaction:** Onset of an illness, distinct from the underlying and/or comorbid disease, occurring usually within the first 48 hours after exposure to an allergy-causing substance with involvement of skin and/or mucosal tissue (eg, local areas of hives, itch, rash, flush, or mildly swollen lips, tongue, and/or uvula), respiratory tract, CV system, and/or gastrointestinal symptoms. The symptoms associated with (non-serious) hypersensitivity do not require immediate intervention (steroids or epinephrine) to prevent deterioration of cardiorespiratory function, ie, they are not life-threatening.

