4.6.2 Adverse events

4.6.2.1 Definition and Derivations

Adverse events experienced by the participants will be collected throughout the entire study and will be coded using the latest version of MedDRA.

Adverse event data will be categorized according to their onset date into the following study periods:

- AEs occurring during screening:
An AE during screening is defined as an AE with a date of onset \geq date of first screening visit (S1) and $<$ date of the first dose of IP.
AEs occurring during screening will only be listed.
- AEs occurring during treatment period:
An AE during treatment period is defined as an AE with a date of onset \geq day of first dose of IP and \leq date of last dose of IP + 28 days.
- AEs occurring during treatment period and follow-up period:
An AE during treatment period and follow-up period is defined as an AE with a date of onset \geq day of first dose of IP and \leq date of last dose of IP + 84 days.
- AEs occurring after follow-up:
An AE after follow-up is defined as an AE with a date of onset $>$ date of last dose of IP + 84 days.
AEs occurring after follow-up will only be listed.

If an AE has a missing onset date, then unless the stop date of the AE indicates otherwise, this will be considered as an AE during treatment. Similarly, if an AE has a partial onset date, then unless the partial onset date or the stop date indicates otherwise, this will be considered an AE during treatment.

Adverse events of special interest are marked as such in the eCRF.

Adverse events with missing intensity will be assumed to be severe. Events with missing relationship to study medication per the investigator will be assumed to be related. If no information about seriousness is available, the AE will be considered serious.

An infusion-related reaction (as assessed by the investigator) is defined as an AE with a PT of “Infusion related reaction”.

An infection is defined as an AE within the SOC infections and infestations.

Opportunistic infections and serious non-opportunistic infections are identified by the investigator.

[figure not shown]
Hypersensitivity is defined as adverse events with MedDRA PT = “Hypersensitivity” and Lower level term (LLT) = “Hypersensitivity reaction”.

Herpes zoster is further classified according to the information given on the eCRF form “HERPZOS” as follows:

HZ Category	Cutaneous/Skin Involvement	Any organ involvement other than cutaneous/skin	Dermatome rule

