This summary will not be presented by SOC but by AESI category

(Serious non-opportunistic infections, opportunistic infections, herpes zoster, tuberculosis including latent tuberculosis, malignancy and MACEs [Cardiovascular outcome events are reported by investigators]).

- Any other significant AE

This summary is presented for AEs during treatment and follow-up period only. This summary will not include the EAIR per 100 patient years.

- Any AE by time interval for the first onset of event

This summary is presented for AEs during treatment period only. This summary will not include the EAIR per 100 patient years.

The time to first onset of a serious non-opportunistic infection during treatment period and time to first onset of herpes zoster during treatment period is presented as Kaplan-Meier plots including the number of participants at risk at each visit.

Furthermore, the number and percentages of subjects with herpes zoster (and possible other AESIs) are summarized for events during treatment and follow-up period, during treatment period (overall and by time intervals). The following subcategories are also considered in this summary: SAE (including events with outcome of death), AE leading to discontinuation of IP, and AE by maximum intensity (mild, moderate, and severe).

The number and percentage of participants with at least one anaphylaxis, hypersensitivity, and infusion-related reaction (as reported by the investigator), respectively, is summarized overall as well as for the following respective subcategories: SAE (including events with outcome of death), AE leading to discontinuation of IP, and AE by maximum intensity (mild, moderate, and severe).

Infections, opportunistic infections and serious non-opportunistic infections, are summarized with the same subcategories as given above.

Key subject information for participants with an AE with outcome of death, participants with serious AEs, participants with an AE leading to discontinuation of IP, participants with AESIs, and ADA positive participants with AEs, respectively, is provided during treatment and follow-up period.

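### The SAP's two-condition coding rule for hypersensitivity can leave events with the same preferred term out of the dedicated summary and the by-timepoint analysis of a named identified risk

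*SAP*

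**What the plan says.** SAP 4.6.2.1 gives the only hypersensitivity rule in the readable text. It states that "Hypersensitivity is defined as adverse events with MedDRA PT" must equal Hypersensitivity, and it adds a second requirement with the words "and Lower level term (LLT"), whose value must be Hypersensitivity reaction. Both must hold. A few lines earlier, the same section identifies an infusion-related reaction by its PT alone.

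The rule feeds two outputs:

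- SAP 4.6.2.2 plans a summary of participants with "at least one anaphylaxis, hypersensitivity, and infusion-related reaction (as reported by the investigator"), broken down by seriousness, discontinuation of study drug and maximum intensity.
- SAP 4.6.2.1 defines a by-timepoint analysis for the same three reaction types.

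The protocol treats hypersensitivity as an established risk. Section 1.3.3 says "Upper respiratory tract infection, bronchitis, respiratory tract infection, hypersensitivity, anaphylactic reaction, and infusion related reaction are identified risks for anifrolumab", and Table 1 lists the same three reaction types as identified risks. Appendix S defines a hypersensitivity reaction clinically, by timing and organ involvement, with examples such as "local areas of hives, itch, rash, flush, or mildly swollen lips, tongue, and/or uvula".

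**The concern.** A dedicated table for an identified risk should contain at least every event coded to the PT of that name. Here it need not. The extra LLT condition makes inclusion depend on which lower level code the event received, and the SAP gives no reason for treating hypersensitivity more narrowly than infusion-related reactions.

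Two things are at stake. First, the table and the by-timepoint display that a safety reader would consult for this risk can undercount it, including its serious, discontinuation and severity sub-rows. Second, the report can disagree with itself: the SOC/PT table and the dedicated table could give different participant counts under the same name, with the smaller count in the dedicated one.

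**Working it through.** The documents give no hypersensitivity rate or count, so there is no planned figure to reproduce. The check is mainly a comparison of rules.

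**Step 1: what the conjunction does.** Let A be the events with PT Hypersensitivity, and B the events with LLT Hypersensitivity reaction. The SAP counts A and B together, which is a subset of A. Either every event in A also has that LLT, and the condition is redundant, or some do not, and they are dropped. In neither case does the condition add an event.

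**Step 2: the neighbouring rule.** For infusion-related reactions, the PT is sufficient. The two rules stand in the same section and feed the same summary, but only one has an LLT filter.

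**Step 3: is there another way in?** Adverse events of special interest are marked in the eCRF (SAP 4.6.2.1), but hypersensitivity is not on that list (Protocol 6.3). The readable text shows no wider term list, standardised query or adjudication for it.

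**Step 4: where dropped events remain visible.** SAP 4.6.2.2 tabulates all adverse events, serious events, events leading to discontinuation and events by maximum intensity by SOC and PT. An event left out by the LLT filter is still in those tables. The gap is confined to the dedicated summary and the by-timepoint analysis, and that is how the two counts can differ.

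**Step 5: illustration only.** Suppose 130 participants per arm (260 randomised 1:1), true rates a on anifrolumab and p on placebo for the PT, and a share c of those participants counted under the required LLT, equal in both arms. Then:

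- expected counts are 130 × a × c and 130 × p × c;
- the risk difference is (a − p) × c;
- the chance of counting nobody in the anifrolumab arm is (1 − a × c)^130.

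The values of a, p and c are all assumed.

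| a vs p | c | Expected counts | Risk difference (points) | Chance of zero on anifrolumab |
|---|---|---|---|---|
| 3% vs 1% | 1 | 3.9 vs 1.3 | 2.0 | 1.9% |
| 3% vs 1% | 0.5 | 1.95 vs 0.65 | 1.0 | 14.0% |
| 3% vs 1% | 0.25 | 0.97 vs 0.33 | 0.5 | 37.6% |
| 5% vs 2% | 1 | 6.5 vs 2.6 | 3.0 | 0.1% |
| 5% vs 2% | 0.5 | 3.25 vs 1.30 | 1.5 | 3.7% |
| 5% vs 2% | 0.25 | 1.62 vs 0.65 | 0.75 | 19.5% |
| 10% vs 4% | 1 | 13.0 vs 5.2 | 6.0 | below 0.1% |
| 10% vs 4% | 0.5 | 6.5 vs 2.6 | 3.0 | 0.1% |
| 10% vs 4% | 0.25 | 3.25 vs 1.3 | 1.5 | 3.7% |

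The table shows only the mechanics: counts and the absolute difference scale with c, while the risk ratio does not change. It says nothing about the likely value of c.

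**The case against.** The strongest defence is that the LLT is not arbitrary. It matches the term that Appendix S defines for this study. Protocol 6.4.6 prefers diagnoses to lists of signs where possible, and the summary is described as investigator-reported. On that view the rule counts investigators' diagnoses made under the protocol's own name, and a reaction recorded that way is counted. This stands, and it is why events can be missed rather than must be. It does not justify the filter, because an investigator-reported event under another LLT of the same PT is still excluded.

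A reader might infer that the SAP discards the reactions Appendix S describes, such as hives or angioedema after an infusion. The documents do not support that:

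- Nothing disappears from safety reporting, because the events stay in the SOC/PT tables, and participants with serious events or events leading to discontinuation also have key information presented.
- Appendix S defines angioedema separately, so its absence from a hypersensitivity row is not in itself a contradiction.
- Appendix S has a residual category for other reactions during or within 24 hours of an infusion, so some events may be counted as infusion-related reactions if coded to that PT.

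Nor does the count depend directly on the investigator's exact words. An LLT is a coded term: the reported text is collected (Protocol 6.4.3) and then classified by a coding team (Protocol 9.4), under conventions the documents do not show.

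Finally, a figure just before the sentence is not shown in the text reviewed, and parts of the SAP are redacted. The absence of a wider rule is therefore a statement about the readable text only. The sentence itself is complete.

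**Conclusion.** The concern holds in a limited form. As written, SAP 4.6.2.1 can exclude events coded to PT Hypersensitivity from the two outputs dedicated to that risk, and it can make those outputs disagree with the general PT row. This follows from the wording and needs no assumption about rates. For anything to be lost in practice, at least one event must reach the PT through a different LLT, and the documents neither confirm nor exclude that.

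The size of the undercount cannot be determined. A reader might also infer that the rule biases the comparison towards no difference. That would require a higher true rate on anifrolumab and equal capture in both arms, and the documents establish neither for hypersensitivity. The summaries are descriptive, and no efficacy conclusion depends on them.

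**What to change.** Before unblinding, delete the LLT condition in SAP 4.6.2.1 so that PT Hypersensitivity alone qualifies, as PT alone already does for infusion-related reactions. Apply the same definition in the 4.6.2.2 summary and in the by-timepoint analysis. If the count under the protocol's own term is of interest, keep the LLT-restricted count as a sub-row.

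The cost is one line of SAP text and, if wanted, one extra row; no new data are needed. The downside is that the row may include some allergies unrelated to the study drug.

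A broader row tied to Appendix S is optional. Its terms, including whether angioedema belongs, are for the sponsor to decide. It involves a real trade-off: Appendix S requires the illness to be distinct from the underlying disease, and a term list with a time window cannot apply that test in SLE, where rash is itself a disease manifestation.

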#### **4.3 Treatment period**

Procedures during the Treatment Period will be performed according to the Treatment Period Study Plan (Table 4), from Randomisation (Week 0) to Week 52. The participant-reported outcome assessments should be completed by the participant (unassisted by spouse, family members or friends) prior to all other evaluations, and prior to the infusion, as disease assessments/clinical evaluations may confound the results.

Before scheduling the Randomisation (Day 1) visit, ensure notification from the DACRT has been received, confirming that participant meets disease activity eligibility (Inclusion Criterion No. 9, 10 and 11). The DACRT will review all data necessary to characterize participant SLE in relation to the SLEDAI-2K, BILAG-2004, and PGA assessments (including central laboratory results).

On Day 1, ensure participant meets eligibility criteria, including Day 1 assessments according to the Treatment Period Study Plan (Table 4). Participants confirmed to be eligible will be randomised. Investigational medicinal product (anifrolumab or placebo) should be administered the same day the investigational medicinal product kit number is assigned and the same day all randomisation study procedures are performed.

Participants will have scheduled visits at 4-week ( $\pm 7$  days) intervals to complete protocol-specified assessments and investigational medicinal product administration according to the Treatment Period Study Plan (Table 4). From Week 4 through Week 48, Investigational medicinal product (anifrolumab or placebo) administration and required study procedures are preferred to be completed in the same day, but are also allowed to be completed within 24 hours if needed.

The last dose of investigational medicinal product will be administered on Week 48. At Week 52, participants will have an End of Treatment (EOT) visit. For participants who prematurely discontinue investigational medicinal product and are not willing to continue to participate in the study refer to Section 3.9 and Section 4.3.1.

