3.3 General Considerations

- Summary tables are produced by treatment group (Anifrolumab 300mg and Placebo) unless otherwise stated. Total columns are produced only for tables of study population data, unless otherwise stated.
- Continuous variables are summarized by the number of non-missing observations, mean, standard deviation (SD), median, and the minimum and maximum as appropriate.
- Log-transformed continuous variables are summarized in a similar manner. The geometric mean and coefficient of variation (CV%), median, minimum and maximum are

presented as appropriate. In addition, the relative change from baseline is calculated by back-transforming the change from baseline of the logarithmic variable as necessary.

- Categorical variables are summarized as counts (n) and percentages (%). Unless otherwise stated, percentages are calculated using the relevant analysis set population total by treatment group as the denominator. Percentages are rounded to one decimal place; except 100% which are displayed without any decimal places. Percentages are not to be presented for zero counts.
- If a model is used to estimate the treatment difference, the corresponding confidence interval (CI) according to the model is presented. Otherwise, the unadjusted CI is used.
- Mean, SD, medians, 1st quartile and 3rd quartile are rounded to one additional decimal place relative to the original data, the maximum, minimum will be displayed with the same accuracy as the original data and the CV% is presented with 1 decimal place. The statistics are displayed in the order of n, mean, minimum, first quartile (optional), median, third quartile (optional), maximum. 95% CIs are presented for treatment comparison to one more decimal place than the raw data. For the confirmatory treatment comparisons, p-values will be reported to 3 decimal places. Percentages (proportion) will be rounded to one decimal place.
- Summaries are provided by time point of assessment where appropriate. Where summaries are by time point, study day is calculated in relation to the date of first dose of study treatment. For assignment of data to time points using the visit windows, study day is calculated in relation to the date of first dose of investigational product.
- Study Day 1 is defined as the day of first study drug administration.
- Study Days prior to the date of first study drug administration, are defined as:
(Date of assessment – date of first administration of IP)

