Cutaneous Localized*	Yes	No	[≤ 3 contiguous unilateral dermatomes selected]
Cutaneous Disseminated	Yes	No	[> 3 contiguous unilateral dermatomes selected] or [non-contiguous dermatomes selected] or [dermatomes on left and right selected and/or bilateral selected]
Visceral Disseminated	Yes/No	Yes	[No rule]

* Cutaneous Localized is defined as below:

- CUTANEOUS/SKIN INVOLVEMENT = “YES”
- All affected dermatomes must be either “RIGHT” or “LEFT” not a mix of either or “BOTH”
- No more than 3 dermatomes are affected
- There is no other organ involvement
- There is an unbroken chain of affected dermatomes in the order that is presented in the image below.
 - The order is: V2, [(V1, V3) or (V3, V1) or (V1) or (V3)], C2, C3, C4, C5, C6, C7, C8, T1, T2, T3,... – T12, L1 – L5, S1 – S5

Adverse events during treatment are also presented by time intervals of the first onset of the event. For this analysis, repeated events with the same PT are not considered (i.e., if a participant has more than one event with the same PT, only the event with the earliest date of onset is used). For partial or missing dates, the rules as described above are used, i.e., the AE is considered as an AE during treatment unless the available information indicates otherwise and as occurring in the earliest possible time interval given the available (start and stop) date information. The following time intervals are defined:

- Day 1 to < Week 12:
AEs with date of onset \geq date of first administration of IP and < date of first administration of IP plus 84 days
- Week 12 to < Week 24:
AEs with date of onset \geq date of first administration of IP plus 84 days and < date of first administration of IP plus 168 days
- Week 24 to < Week 36:
AEs with date of onset \geq date of first administration of IP plus 168 days and < date of first administration of IP plus 252 days
- Week 36 to < Week 48:
AEs with date of onset \geq date of first administration of IP plus 252 days and < date of first administration of IP plus 336 days
- \geq Week 48:
AEs with date of onset \geq date of first administration of IP plus 336 days

Exposure-adjusted incident rate (EAIR) per 100 patient years is defined as

Sum of subjects with the event/[sum across subjects' time at risk for the event
/(365.25*100)]

Where time at risk is time to first event for subjects who experienced the event during the analysis period and time during the analysis period for subjects who do not experience the event.

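### The table of adverse events by time of first onset has a final interval about a third as long as the others, a fixed denominator and no exposure adjustment, so a constant risk would read as a falling one

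*SAP*

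**What the plan says.** SAP 4.6.2.1 says: "Adverse events during treatment are also presented by time intervals of the first onset of the event". The first interval runs from first dose to just before the "date of first administration of IP plus 84 days". The next three are also 84 days wide, and the final one starts at the "date of first administration of IP plus 336 days" with no upper edge of its own. Repeats of a preferred term in one participant are dropped: "only the event with the earliest date of onset is used". The same section closes the treatment period for adverse events at the "date of last dose of IP + 28 days". Protocol 4.3 fixes the last dose: "The last dose of investigational medicinal product will be administered on Week 48".

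SAP 3.3 sets the default that "percentages are calculated using the relevant analysis set population total by treatment group as the denominator", and SAP 4.6 makes the safety analysis set the relevant one. SAP 4.6.2.1 and 4.6.2.2 state no exception for this table and no number at risk per interval. SAP 4.6.2.2 lists the summary as "Any AE by time interval for the first onset of event", restricts it to the treatment period and excludes the EAIR from it. The EAIR is otherwise the default for treatment-period events, but over the whole period. The same section also splits herpes zoster, and possibly other events of special interest, by time interval as numbers and percentages.

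**The concern.** A display split by time of onset invites the reader to ask whether events come early or late. Here the columns differ in length, and participants who have left the on-treatment window, or who already had the event in question, stay in the denominator. An unchanging risk then looks like a risk that fades, with a sharp drop after Week 48. A real late increase could be hidden in the same way. For most adverse events the SAP plans no other display of onset time with a risk set, so nothing beside the table would correct the impression.

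**Working it through.** **Interval widths.** The plan's own figure for the start of the final interval is 336 days after first dose. It reproduces three ways:
- four intervals of 84 days: 4 × 84 = 336
- 13 doses every 4 weeks: 12 × 28 = 336
- Week 48 is study day 337 in SAP Table 1: 337 − 1 = 336

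On schedule the last dose is at first dose + 336 days, and the treatment period for adverse events ends at 336 + 28 = 364 days. Counting both end days, the final interval holds 364 − 336 + 1 = 29 days. If the Week 48 dose moves by the ±7-day visit window (Protocol Table 4), it holds 22 to 36 days. Relative width: 29/84 = 0.345.

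**Expected percentages under constant risk.** The documents give neither event rates nor discontinuation rates, so both are assumptions shown over a range. Let h be a constant hazard of first event and m a constant hazard of leaving the on-treatment window, with m = −ln(1 − d)/365 per day for a proportion d stopping by Week 52. The share of all treated participants with first onset between days a and b is

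h/(h + m) × [exp(−(h + m)a) − exp(−(h + m)b)],

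with edges 0, 84, 168, 252, 336 and 365 days. For example, at h = 10 per 100 patient-years (PY) and m = 0, the first interval gives 1 − exp(−0.10 × 84/365.25) = 2.27%, and the last gives exp(−0.10 × 336/365.25) − exp(−0.10 × 365/365.25) = 0.72%.

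| Hazard per 100 PY | Stopping by Week 52 | Percentage in the five intervals | Last/first | Fourth/first |
|---|---|---|---|---|
| 5 | 0% | 1.14, 1.13, 1.12, 1.10, 0.38 | 0.33 | 0.97 |
| 5 | 20% | 1.11, 1.05, 0.98, 0.92, 0.31 | 0.27 | 0.83 |
| 10 | 0% | 2.27, 2.22, 2.17, 2.12, 0.72 | 0.32 | 0.93 |
| 10 | 20% | 2.22, 2.06, 1.91, 1.77, 0.58 | 0.26 | 0.80 |
| 30 | 10% | 6.59, 6.00, 5.47, 4.98, 1.61 | 0.25 | 0.76 |
| 100 | 0% | 20.55, 16.32, 12.97, 10.31, 3.04 | 0.15 | 0.50 |
| 100 | 20% | 20.05, 15.13, 11.42, 8.62, 2.46 | 0.12 | 0.43 |

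The true hazard is constant in every row. The drop in the last column comes mainly from width and needs no dropout. The fall over the first four columns comes only from discontinuation and from first events using up the risk set.

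**In participants.** With about 130 per arm (260 randomised 1:1, SAP 3.2), the first-to-fourth fall at 10 per 100 PY with no dropout is (2.27 − 2.12)% × 130 = 0.2 of a participant. At 30 per 100 PY with 10% stopping it is (6.59 − 4.98)% × 130 = 2.1.

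**Masking.** Ignoring depletion, the hazard in the last interval would have to rise by 84/29 = 2.9 times for its percentage to equal the first.

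**Between arms.** Take an equal hazard of 20 per 100 PY, with 10% stopping in a year in one arm and 25% in the other. Weeks 36 to 48 then read 3.60% against 3.11%, a gap of 0.49% × 130 = 0.6 of a participant.

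**After the change.** Dividing events by person-time in the interval gives the same rate in all five intervals in each row: 10.0 throughout at 10 per 100 PY, and 30.0 throughout at 30.

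**The case against.** The strongest reply is that this is one supplementary descriptive table on which no test or decision depends, and that the SAP covers much of the need elsewhere. SAP 4.6.2.2 plans Kaplan-Meier plots with numbers at risk for time to first herpes zoster and first serious non-opportunistic infection. SAP 4.6.1.2 reports exposure in 4-week steps by arm and a Kaplan-Meier plot of time to discontinuation, so the number still on treatment at each interval edge can be looked up. The whole-period EAIR, with a confidence interval for the arm difference, already adjusts the overall comparison for exposure.

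This stands, and it narrows the point. It does not remove it. The exposure tables do not show who is still event-free for a given term, and other adverse events have no onset display with a risk set.

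A reader might infer that the table shows rates that must fall with time on drug. It does not: it shows percentages of participants, and a hazard that truly rises could offset or hide the fall. A reader might also infer that the arm comparisons are biased. The structure is the same in both arms, so that needs a difference in discontinuation or in earlier events. The documents give no such difference, and the example above amounts to less than one participant.

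Two cautions about the remedy also stand. The last interval holds at most about 130 × 28/365.25 = 10 patient-years per arm, so a single event reads as 10 per 100 PY with an exact 95% interval of about 0.25 to 56. And when participants differ in risk, the highest-risk ones have their first event early, so even an interval EAIR can decline somewhat, especially for any adverse event.

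**Conclusion.** The point holds for the time trend within an arm. Under a constant hazard the last column is about a third or less of the first: 0.33 down to 0.12 over assumed hazards of 5 to 100 per 100 PY and 0 to 20% discontinuation. Over the four equal intervals the fourth-to-first ratio runs from 0.97 down to 0.43. That fall is negligible for rare events and material for common ones or heavy dropout. The results rest on on-schedule dosing, constant hazards, and the SAP 3.3 default denominator applying because no exception is stated.

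The documents do not support reading this as a general bias between arms, or as leaving the timing of herpes zoster and serious non-opportunistic infection unexamined. It is a worthwhile, inexpensive improvement to a descriptive safety table and has no bearing on the efficacy conclusion.

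**What to change.** In SAP 4.6.2.1 and 4.6.2.2:
- For each interval, show the number still in the on-treatment window and event-free for that term at its start. Use that number, or person-time in the interval, as the denominator.
- Report an interval EAIR per 100 patient-years with a 95% CI, at least for any adverse event and for the herpes zoster and special-interest summary.
- Remove the exclusion of the EAIR from the time-interval summary.
- Footnote the actual length of the final interval: about 28 days on schedule against 84 for the others.

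The dates are already collected, and time at risk and the EAIR are already defined in SAP 4.6.2.1. The cost is SAP wording and modest extra programming for term-specific person-time by interval, in both the general table and the herpes zoster summary. Confidence intervals in the last column will be wide and should be read that way. If the full change is not wanted, printing the number on treatment at the start of each interval and adding the footnote would remove the worst of the misreading.
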